3.3 Dosing

Etanercept or placebo will be administered in three separate doses (0.8 mg/kg subcutaneously, maximum 50 mg) at 1 week intervals with the first dose concurrent with IVIG or within 48 hours of initiating IVIG.

Rationale for extended therapy: Current KD treatment with IVIG and ASA in the United States is based on efficacy comparison with ASA alone⁸. Subsequently, studies showed no difference in efficacy between IVIG (400 mg/kg) given in 4 separate doses on consecutive days versus a single infusion IVIG (2 gm/kg) over 10 hours¹². Nevertheless, data across more than 2 decades show that coronary artery involvement increases during the 2 week period following treatment. Furthermore, refractoriness to IVIG can manifest up to 2 weeks after completion of IVIG. Inoue¹³ et al showed some increased benefit of continuing oral steroids until inflammatory parameters such as CRP normalized. In that study, laboratory studies were performed at least twice weekly. Normalization of CRP level in the placebo group (receiving IVIG and ASA, no corticosteroid) occurred in 9.0 days (median) range 4 to 42 and mean 11.2 ± 6.2 days. These data, along with the their results showing some mild efficacy by more prolonged corticosteroid therapy, strongly support the contention that anti-inflammatory therapy for KD should be extended to near 3 weeks, provided therapy is convenient and low-risk. Accordingly, we will maintain treatment for 3 weeks to cover all patients within this vulnerable period. As our pilot data suggest that Etanercept levels are maintained at a near steady-state by week 2, we will give the final dose at $14 \text{ days} \pm 2$ in order to maintain levels at least 3 weeks.

4 Patient Population and Sample Size

196 study participants will be recruited from the four participating medical center admissions for suspected Kawasaki Disease with IVIG administration. Seattle Children's Hospital is the coordinating site for the study. Most patients will be on the Cardiology or General Medicine Service.

4.1 Inclusion criteria:

Identification of patients with KD:

The American Academy of Pediatrics and the American Heart Association have published guidelines for epidemiological case definition. KD treatment, including IVIG and aspirin, is recommended for patients fitting these criteria. Generally, supportive laboratory data also exist including elevation of erythrocyte sedimentation rate and C reactive protein (CRP > 3.0 , although usually much higher). Thrombocytosis (platelet count $> 500,000$) usually occurs in the second week.

- Patients in this study (age 2 months to 20 years) will fit the standard epidemiological definition of acute KD as recommended by the joint AHA/AAP guidelines or fit criteria for diagnosis of incomplete KD as described below. Patients will be enrolled only after a clinical decision to treat with IVIG has been made by the treating physician.
- Patients may be enrolled if they begin IVIG infusion within 10-13 days of onset of illness with day 1 defined as the first day of fever. A patient may be enrolled with greater than 10 days of fever upon written approval or email confirmation from the study Principal Investigator ([name]) on a case by case basis.
- Parents of subject or non-minor subject must be able and willing to give written informed consent and comply with the requirements of the study protocol and must authorize release and use of protected health information.

Patients will fit American Heart Association, American Academy of Pediatric guidelines for diagnosis of Kawasaki Disease

Fever persisting at least 5 days†

Presence of at least 4 principal features:

- 1) Changes in extremities
Acute: Erythema of palms, soles; edema of hands, feet
Subacute: Periungual peeling of fingers
- 2) Polymorphous exanthem
- 3) Bilateral bulbar conjunctival injection without exudate
- 4) Changes in lips and oral cavity: Erythema, lips cracking, strawberry tongue, diffuse injection of oral and pharyngeal mucosae
- 5) Cervical lymphadenopathy (1.5-cm diameter), usually unilateral

Patients with fever at least 5 days and 3 principal criteria can be diagnosed with Kawasaki disease when coronary artery abnormalities are detected by 2 dimensional echocardiography (see section on Echocardiography). A qualifying echocardiogram is defined as coronary artery z score ≥ 2.5 in the proximal coronary artery or left anterior descending, or aneurysm by Japanese Ministry of Health criteria.

CONFIDENTIAL

This material is the property of the Seattle Children's Research Institute. Do not disclose or use except as authorized in writing by the study sponsor-investigator.

Patients with fever at least 5 days and 2-3 principal criteria without coronary artery abnormalities can be diagnosed with Kawasaki Disease when the patient has a CRP of 3.0 mg or greater and 3 or more of the supplementary lab criteria listed below:

albumin <3.0 g/dL
anemia for age
elevation of alanine aminotransferase
platelets after 7 days >450 000/mm³
white blood cell count >15 000/mm³
urine >10 white blood cells/high-power field

† In the presence of all 5 principal criteria, Kawasaki disease diagnosis can be made on day 4 of illness.

4.2 ***Exclusion Criteria***

1. Laboratory Criteria: Any laboratory toxicity, at the time of the screening visit or at any time during the study that in the opinion of the Investigator would preclude participation in the study or:
 - a. Platelet count < 100,000/mm³
 - b. WBC count < 3,000 cells/mm³
 - c. Hemoglobin, hematocrit, or red blood cell count outside 30% of the upper or lower limits of normal for the Lab
2. General Exclusion Criteria
 - a. Subject is currently enrolled in another investigational device or drug trial(s), or subject has received other investigational agent(s) within 28 days of baseline visit.
 - b. Female subjects diagnosed with KD 12 years of age and older.
 - c. Subjects who have known hypersensitivity to Enbrel or any of its components or who is known to have antibodies to etanercept
 - d. Prior or concurrent cyclophosphamide therapy
 - e. Treatment with any TNF α antagonist or steroid within 48 hours prior to initiation of IVIG
 - f. Concurrent sulfasalazine therapy
 - g. Active severe infections within 4 weeks before screening visit, or between the screening and baseline visits.
 - h. SLE, history of multiple sclerosis, transverse myelitis, optic neuritis, or chronic seizure disorder
 - i. Known HIV-positive status or known history of any other immuno-suppressing disease.
 - j. Any mycobacterial disease or high risk factors for tuberculosis, such as family member with TB or taking INH. * (see below)
 - k. Untreated Lyme disease.
 - l. Severe comorbidities (diabetes mellitus requiring insulin, CHF of any severity, MI, CVA or TIA within 3 months of screening visit, unstable angina pectoris, uncontrolled hypertension (sitting systolic BP > 160 or diastolic BP \geq 100 mm Hg), oxygen-dependent severe pulmonary disease, history of cancer within 5 years [other than resected cutaneous basal or squamous cell carcinoma or in situ cervical cancer])
 - m. Exposure to hepatitis B or hepatitis C or high risk factors such as intravenous drug abuse in patient's mother, or history of jaundice (other than neonatal jaundice).* SLE, history of multiple sclerosis, transverse myelitis, optic neuritis or chronic seizure disorder.

CONFIDENTIAL

This material is the property of the Seattle Children's Research Institute. Do not disclose or use except as authorized in writing by the study sponsor-investigator.

- n. Use of a live vaccine (Measles Mumps Rubella or Varicella) 30 days prior to or during this study with the exception that a patient who has received Influenza mist vaccine may be enrolled after 14d from administration of the vaccine.
- o. Any condition judged by the investigator to cause this clinical trial to be detrimental to the patient
- p. History of non-compliance with other therapies
- q. Must not have received immunosuppressive agents for at least three months prior to enrollment.

*Note, liver enzymes, AST or ALT are frequently elevated in KD, and will not be used as an exclusion.

* PPD testing will not be performed in these patients. Reactivation of chronic granulomatous disease including tuberculosis from chronic treatment with TNF α antagonists is a valid safety concern.³¹ The risk of TB reactivation for patients on etanercept therapy still requires clarification. A recent review at Cook County and Rush Hospital in Chicago showed that none of the 48 patients with positive PPDs who were treated with etanercept for average of 17 months developed active TB⁵³. Additionally, Mohan et al reported the earliest reactivation occurred after 1 month of initiating etanercept with a mean of 11.5 months⁵⁴. Use of additional immunosuppressive agents other than etanercept was a risk factor. Our cohort will receive a very short course (~ 2 weeks) of etanercept and will not receive other immunosuppressive drugs, thereby markedly reducing the already very low risk of TB in this population. For instance, the incidence of TB in King County, WA in children is 1 -2.5/100,000 or 8-12 per year. To be effective in acute Kawasaki Disease, etanercept must be given at the same time or immediately after IVIG treatment. We cannot delay while awaiting mandatory 48-72 hours for results of skin testing. The new Quantiferon gold test for TB is not yet widely available (and not in Seattle) and would still require at least 24 hours. We have considered placing TB skin testing after initial dose and discontinuing if positive. However, it is likely that TNF- α antagonism could affect the test and provide a false negative. Therefore patient exclusion will be performed based on high risk history, such as immediate family or household member with positive PPD.

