Pentoxifylline is a methyl-xanthine compound and phosphodiesterase inhibitor that inhibits TNF- α messenger RNA transcription. A single study showed a trend towards improved prevention of CAD when using pentoxifylline in addition to ASA and low dose IVIG, compared to ASA and low dose (IVIG 1 gm/kg total)²⁹. The study had relatively few patients and was likely not empowered to detect significant differences between groups. Furthermore, the subsequent development of more specific TNF antagonists relegates this strategy to obscurity. The study does suggest that early and prolonged antagonism of the TNF- α pathway might prevent CAD in KD patients.

The TNF antagonists fall into 2 classes: monoclonal antibodies and soluble receptors³⁰. Etanercept (Enbrel®, [name]) is a soluble TNF receptor, while infliximab (Remicade®, Horsham, PA) and adalimumab (Humira®, Abbott Park, ILL) are monoclonal antibodies against TNF. These agents are now widely used for the treatment of rheumatoid arthritis including juvenile onset and other inflammatory diseases. As of December 2006, more than 400,000 patients worldwide had been treated with etanercept and more than 500,000 had been

CONFIDENTIAL

This material is the property of the Seattle Children's Research Institute. Do not disclose or use except as authorized in writing by the study sponsor-investigator.

treated with infliximab³¹. As of August 31, 2004, 10,050 patients with RA had enrolled in adalimumab clinical trials worldwide³¹. Infliximab is used for inflammatory bowel disease in children, while Etanercept is FDA approved for use in JRA for children down to 2 years of age.

1.2 *Investigational Agent*

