5.5 Prior and Concomitant Therapy

The following medical therapies are not permitted for study participation:

- Treatment with any TNF α antagonist or steroid within 48 hours prior to initiation of IVIG
- Current use of an investigational device or drug trial(s), or receipt of other investigational agent(s) within 28 days of baseline visit
- Prior or concurrent cyclophosphamide therapy
- Concurrent sulfasalazine therapy
- Concurrent isonicotinic acid hydrazide therapy
- Any live vaccine 30 days prior to, or during the study. Patient may be enrolled in the study 14 days after administration of Influenza mist vaccine.
- Prior (within 3 months preceding enrollment) or concurrent use of immunosuppressive agents

In addition, any medical therapies that may cause harm to the patient, as judged by the patient's physician on a case-by-case basis, will not be permitted.

CONFIDENTIAL

This material is the property of the Seattle Children's Research Institute. Do not disclose or use except as authorized in writing by the study sponsor-investigator.

IVIG (2 g/kg) and aspirin (80-100mg/kg Q6 hr until afebrile then 3-5 mg/kg/day) are standard treatment regiments for acute Kawasaki Disease, their concomitant therapy is to be expected and permitted.

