Treatment with high dose steroids and/or infliximab during the course of the study is permitted if recommended by Rheumatology for the treatment of recurrent Kawasaki Disease.

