6.5 Visit 5 (Day 44 ± 4 days)- Clinic

A physical exam and a blood draw (approximately 7 cc) are required. . The blood sample is sent to the laboratory for the tests listed in schema. An Echo/ EKG is performed. No study drug is administered.

6.6 Treatment for refractoriness to IVIG.

All patients who fit the requirements for refractoriness to IVIG (see section 3.1) will receive standard clinical treatment as determined by the attending physician. Standard treatment is usually a second dose of IVIG, and is defined in the American Heart Association guidelines. Retreatment with IVIG will not interrupt the study and study medication should still be administered.

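### The TB-testing waiver says children will get no other immunosuppressives, but section 6 permits steroid or infliximab rescue, and no visible rule says whether study drug stops once infliximab starts

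*Combined protocol and SAP*

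**What the plan says.** The note on PPD testing in section 4.2 explains why no skin test is done. On reactivation it reports: "Use of additional immunosuppressive agents other than etanercept was a risk factor". It then says that this cohort "will not receive other immunosuppressive drugs, thereby markedly reducing the already very low risk of TB in this population". It gives other grounds as well: the course is short, local incidence is low ("the incidence of TB in King County, WA in children is 1 -2.5/100,000"), treatment cannot wait for a result, a test after dosing could be falsely negative, and children with a high-risk history are excluded.

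Section 6 (Study Procedures) states: "Treatment with high dose steroids and/or infliximab during the course of the study is permitted if recommended by Rheumatology", for recurrent disease. Section 1.1 explains that "The TNF antagonists fall into 2 classes: monoclonal antibodies and soluble receptors", and places infliximab in the first class and etanercept in the second.

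Section 6.6 (Treatment for refractoriness to IVIG) holds the only visible instruction on study drug after rescue: "Retreatment with IVIG will not interrupt the study and study medication should still be administered".

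Section 5.5 lists therapies that are not allowed for participation. One item is "Prior (within 3 months preceding enrollment) or concurrent use of immunosuppressive agents". A separate item covers any TNF "antagonist or steroid within 48 hours prior to initiation of IVIG".

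**The concern.** The waiver names added immunosuppression as a risk factor and then counts its absence as a reason for reassurance. Section 6 allows that same exposure, so for a rescued child the safety statement given to ethics committees and sites is wrong.

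The second matter is practical. Three weekly doses are scheduled, and nothing visible tells a site what to do with the second or third once infliximab has been given. The treating physician is blinded and cannot know whether the next syringe adds TNF blockade. One site may continue by analogy with IVIG retreatment, while another may stop because of section 5.5. The protocol treats this area as sensitive: it excludes children given a TNF antagonist shortly before IVIG, makes serious infection a specific safety focus (section 3.2), and notes that monoclonal antibodies may be the more potent inhibitors (section 1.2).

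**Working it through.** No figure in the plan rests on this point, so there is none to reproduce. The check compares the texts and then gauges scale.

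**Texts side by side**

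| Place | Content | Bearing |
|---|---|---|
| 4.2, PPD note | No other immunosuppressives; no exception | Untrue for a child rescued under section 6 |
| 6, Study Procedures | Steroids or infliximab allowed for recurrent disease | Silent on study drug |
| 3.3, 5.2, 6.3, 6.4 | Three weekly doses | No stop condition |
| 6.6, refractoriness | Study drug continues | After IVIG retreatment only |
| 5.5, last bullet | Concurrent immunosuppressives barred | No rescue exception; could be read as a reason to stop |
| 5.5, TNF antagonist or steroid bullet | 48 hours before IVIG only | Does not reach rescue |

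**Children rescued, etanercept arm**

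Inputs: 196 subjects (Study Summary), equal arms, and failure rates of 0.08 and 0.25 (section 4.3; 0.25 in this arm means no drug effect). The share of refractory children given steroids or infliximab is not stated; 10-50% is assumed.

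- Per arm: 196 / 2 = 98.
- At 8%: 98 × 0.08 = 7.84 refractory; × 0.10 = 0.8; × 0.50 = 3.9. About 1 to 4 children.
- At 25%: 98 × 0.25 = 24.5 refractory; × 0.10 = 2.5; × 0.50 = 12.3. About 2 to 12 children.

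These counts cover steroids or infliximab at any time. A hold applies only to infliximab started before dose 3, so it affects fewer children, by an amount the documents do not allow one to estimate.

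**Tuberculosis**

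For 12 children at the quoted incidence:

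- 12 × 1/100,000 = 0.00012 background cases per year.
- 12 × 2.5/100,000 = 0.0003 per year.
- With a tenfold rise (assumed): 0.0012 to 0.003 per year.

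**What a hold can avoid**

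- Infliximab between doses 1 and 2: 2 of 3 doses withheld, 1.6 of 2.4 mg/kg (67%).
- Infliximab between doses 2 and 3: 1 of 3 withheld, 0.8 of 2.4 mg/kg (33%).

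Drug already given stays. With the 115-hour half-life in section 1.4 and first-order decay assumed, the fraction left 7 days after a dose is 0.5^(168/115) = 0.36. Counted from the 50-hour peak, it is 0.5^((168 − 50)/115) = 0.5^(118/115) = 0.49.

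**Adverse event reporting**

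Section 8.1 ends reporting 30 days after the last dose.

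- Only dose on day 0: reporting ends on day 30, before visit 5.
- Dose 3 at the end of its window, day 14 + 3 = 17: reporting ends on day 47. Visit 5 may fall on day 44 − 4 = 40, so a rule ending at visit 5 could cut 47 − 40 = 7 days.

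A hold rule therefore needs the later of the two dates.

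**The case against.** **The protocol does not order double blockade.** A reader might infer from the unbroken schedule that remaining etanercept must be given on top of infliximab. The documents do not support that. The instruction to continue in section 6.6 is limited to IVIG retreatment, and section 5.5 could be read as a reason to stop. What stands is silence, and with it possible variation between sites.

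**Clinical judgement already covers this.** Section 4.5.1 allows withdrawal for health reasons, section 4.5.3 allows emergency unblinding, section 5.5 bars harmful therapies case by case, and the DMC follows infections (section 8.5.1). These lower the risk, but none mentions infliximab or steroid rescue, and none sets a common rule.

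**The rule may exist elsewhere.** Section 8.5.1 refers to a Human Subject section, and the DMC charter is an attachment. Neither is in the available text. The absence claim is therefore limited to visible text; the clash between 4.2 and 6 is not affected.

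**No document describes harm from etanercept with infliximab, and the risk-factor sentence covers steroids too.** Both points are true. Holding study drug after infliximab is a clinical choice, based on the two drugs sharing a target. It is reasonable to leave steroids to the investigator.

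**Section 5.5 flatly contradicts section 6.** This also goes too far. Section 6 allows all medications prescribed by primary care providers and names these two rescue options, so permission is the more natural reading. Section 5.5 is ambiguous.

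**Conclusion.** The sentence in section 4.2 is wrong as written for any child rescued with steroids or infliximab. The missing study-drug rule after infliximab is a gap worth closing as a cheap improvement. Overall the point is one for the sponsor to consider.

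The size is small and not derivable. The 1-12 range rests on equal arms of 98, failure rates of 8% to 25%, and an assumed 10-50% rescue share. It should not be read as the number who would have doses withheld, which is smaller. Expected tuberculosis cases stay at or below 0.003 per year even with an assumed tenfold rise, so the gain is a true safety statement and one rule for all sites.

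A reader might also infer that the waiver of testing is unsound. It is not shown to be: the grounds of timing, false negatives, low incidence, short course and history-based exclusion are untouched.

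**What to change.** One amendment with four edits:

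1. **Section 4.2, PPD note.** After the statement that no other immunosuppressives will be received, add: *except as rescue permitted in section 6*.
2. **Section 5.5, last bullet.** Attach the same exception to concurrent use only; leave the three-month bar on prior use as it is.
3. **Section 6, rescue sentence.** Keep the indication (recurrent disease) unchanged and add: *Once infliximab is started, withhold remaining study drug in both arms without breaking the blind. All visits continue, and adverse events are reported through visit 5 or 30 days after the last study drug dose, whichever is later.* Leave study drug after steroids to investigator judgement.
4. **Section 6.6 (Treatment for refractoriness to IVIG).** Add a cross-reference to section 6 for infliximab or steroids.

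No new test, visit or unblinding is needed, and the choice of rescue drug stays with the treating physicians. The case report forms are not visible. If the IVIG retreatment form does not record rescue agent, start date and doses withheld, add one line.

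The cost is a shorter study-drug course in a few children, which slightly dilutes their coronary data. They stay in their randomized group, and a refractory status already reached does not change.

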4.3 SAMPLE SIZE

Calculation of sample size is based on initial IVIG refractory rate at Children's Hospital and Regional Medical Center. The last 200 patients over 4 years admitted to CHRMC 52 patients (26%) required two or more doses of IVIG. Power analyses reveal the following:

Proportion failing in the control group	Proportion failing in the experimental group given Etanercept	N per group needed to achieve 80% power NOTE: TOTAL enrollment = 2 x N
0.25	0.15	270
0.25	0.10	110
0.25	0.05	59
0.25	0.02	42

Sample size 110 is reasonable, considering the potential population and budget. The table below that shows power for a range of effect sizes, holding the N at 110.

The table below provides the relationship between effect size and study power.

Proportion failing in the control group	Proportion failing in the experimental group given Etanercept	N per group	Statistical Power
0.25	0.08	97	80%

CONFIDENTIAL

This material is the property of the Seattle Children's Research Institute. Do not disclose or use except as authorized in writing by the study sponsor-investigator.

The table below provides anticipated numbers of patients eligible from four U.S. and one Canadian Center, and anticipated numbers of recruited patients based on recruitment rates from prior studies. From CHMRC, estimates are based on KD patients per year and our recruitment rate in the pilot study, which enrolled patient in the narrow age range 6 months to 5 years. From Primary Children's in Utah, estimates are based on their recruitment rate and participation in the Pediatric Heart Network "Randomized trial of pulsed corticosteroid therapy for primary treatment of Kawasaki disease". From Milwaukee Children's and Cohen Children's Medical Center, estimates are based on KD admission rate and recruitment rate as adjunctive center for PHN protocols. Sainte-Justine Hospital estimates are based on high enrollment for Bristol-Myers-Squibb sponsored studies evaluating Cardiolite in Kawasaki Patients (Study # 301 (see description under Key Personnel and Sites of Investigation). Each center has clinical research structure and team permanently in place and structured.

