We will test the hypothesis that TNF- α antagonism with etanercept improves the clinical response to standard of care treatment with IVIG and aspirin therapy in KD patients between 2 months and 20 years of age. To test this hypothesis we will perform a double-blinded placebo controlled trial in 196 children with KD and obtain data in order to achieve an orphan designation for etanercept.

Primary Aim

1. Determine if etanercept (0.8 mg/kg, maximum 50 mg) given subcutaneously reduces IVIG refractory rate and retreatment rate in the KD patient population. Our goal is to randomize and complete the trial in 110 patients in the etanercept treatment group and 110 patients in the placebo group.

Secondary Aims

1. Determine if the safety profile differs between the etanercept treated group and the placebo group.
2. Determine if etanercept treatment alters the rate of coronary artery dilation and disease (CAD) defined by z-scores at 2 and 6 weeks after treatment.
3. Determine the pharmacokinetics of etanercept in KD patients

3 Research Design and Methods

We propose a placebo-controlled randomized double blind multi-center study in patients, age 2 months to 20 years, with acute Kawasaki disease. All study investigators will be blinded except for pharmacists.

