The pharmacist and pharmacy technical staff will be not be blinded. The study statistician will provide each site pharmacy with randomization table. Pharmacists will supply each patient with drug or placebo, both provided by Amgen in separate labeled vials. Pharmacists will draw dose in syringes and dispense to nursing for administration. Drug accountability will be monitored by the CRO as described below. Study randomization codes and links to patients will be kept in secure records in pharmacy. All other study personnel involved in administration of drug will be blinded.

6.9 **IVIG Retreatment**

As noted in section 3.1: The primary aim of this study is to determine if Etanercept (Enbrel) 0.8 mg/kg given subcutaneously to patients with acute Kawasaki Disease will reduce the incidence of IVIG refractoriness as defined in the joint American Heart Association and American Academy of Pediatrics Endorsed Clinical Report: "Refractory Kawasaki Disease will be defined as the persistence or recrudescence of fever ($\geq 38.0^{\circ}\text{C}$ or 100.4°F) at least 36 hours after the end of the IVIG infusion"³. Persistent or recrudescent fever is the sole criteria for determining the need for retreatment. The clinical decision can be supported by persistent symptoms and persistent elevation or rebound of inflammatory parameters such as CRP. The protocol requires waiting at least 36 hours after completing the first IVIG dose before initiating the second dose.

7 Statistical Design and Analysis

The primary outcome variable is the Y/N determination of whether the subject is refractory to IVIG treatment, defined as persistence of fever $>38^{\circ}\text{C}$ beyond 36 hours from completion of IVIG treatment, or recurrence of fever within 10 days, and clinical decision to retreat with IVIG. Chi-square testing will be used to compare the proportions of subjects classified as refractory to IVIG treatment between the group randomized to receive Etanercept as an adjunctive therapy and the group randomized to receive placebo. If necessary (due to low cell counts), a Fisher's Exact test can be substituted. Stratified versions of the chi-square and Fisher's tests are available in StatXact (Cytel Incorporated) to allow stratification by center.

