8.5.1 Independent Data Monitoring Committee

The Data Monitoring Committee (DMC) will be composed of a pediatric rheumatologist, and a pediatric cardiologist to oversee the study. Safety data of the 196 patients with regards to adverse events, specifically focusing on infections, will be closely monitored in these patients

- *The DMC will meet at least once every 6 months via telephone conference.*
- *The safety data will be supplied to the DMC by the principal investigators team. .*
- *The DMC will prepare minutes to record the summary of its various meetings.*
- *The DMC will appropriately report its findings and/or recommendations to the PI and regulatory bodies.*

The Data Safety Plan and Data Monitoring Committee (DMC)

The data safety plan for this study is also included in detail in the Human Subject section. The DMC was established and chartered in order to monitor the progress of the pilot study. The DMC will continue this

PRIMARY RESPONSIBILITIES OF THE DMC

The DMC will be responsible for safeguarding the interests of trial participants, assessing the safety of the interventions during the trial, and for monitoring the overall conduct of the clinical trial. The DMC will provide recommendations about stopping or continuing the trial. To contribute to enhancing the integrity of the trial, the DMC may also formulate recommendations relating to the selection/recruitment/retention of participants, their management, improving adherence to protocol-specified regimens and retention of participants, and the procedures for data management and quality control.

The DMC will be advisory to the Principal Investigator. The Principal Investigator will be responsible for promptly reviewing the DMC recommendations, to decide whether to continue or terminate the trial, and to determine whether amendments to the protocol or changes in study conduct are required. The Principal Investigator will be required to forward all DMC recommendations to the IRB.

Members

The DMC will be an independent multidisciplinary group consisting of clinicians, whom collectively have experience in the management of patients with Kawasaki Disease and in the conduct and monitoring of clinical trials. Generally, three pediatric subspecialties deal with KD. These are cardiology, rheumatology, and infectious disease. Each of these subspecialties will be represented on the DMC.

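### The protocol gives two trial sizes, 196 and 110 + 110 = 220, and the power row near 196 (25% vs 8%, 97 per group, 80%) does not reproduce

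*Combined protocol and SAP*

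**What the plan says.** The size 196 appears in the Study Summary (number of subjects) and in three later places:

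- Section 2, hypothesis statement: "To test this hypothesis we will perform a double-blinded placebo controlled trial in 196 children with KD".
- Section 4, opening sentence: "196 study participants will be recruited from the four participating medical center admissions".
- Section 8.5.1: "Safety data of the 196 patients with regards to adverse events".

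The size 110 per group, or 220, appears in three places:

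- Section 2, Primary Aim, directly after the hypothesis statement: "Our goal is to randomize and complete the trial in 110 patients in the etanercept treatment group and 110 patients in the placebo group".
- Section 4.3: "Sample size 110 is reasonable, considering the potential population and budget".
- Section 10, table dividing responsibilities between the PI and the CRO: monitoring is planned for 220 patients.

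Section 4.3 has two tables. The first is headed "N per group needed to achieve 80% power NOTE: TOTAL enrollment = 2 x N" and, for a 25% control failure rate, lists 270, 110, 59 and 42 per group against etanercept rates of 15%, 10%, 5% and 2%. The second is introduced by "The table below that shows power for a range of effect sizes, holding the N at 110" and shows one row: 25% vs 8%, 97 per group, 80% power.

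For the primary analysis, Section 7 states: "Chi-square testing will be used to compare the proportions of subjects classified as refractory to IVIG treatment", with Fisher's exact test if cell counts are low.

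**The concern.** The enrolment target decides when recruitment stops. With two targets in the current text, stopping at 196 or continuing to 220 could each be defended afterwards.

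The effect that the trial was sized to detect is equally unclear. The text settles on 110 per group, which is the 25% vs 10% row of the first table. The row near 196 uses 25% vs 8%. Doubling 97 gives 194, so no row in Section 4.3 corresponds exactly to 98 per group. If the 80% does not belong to 25% vs 8% at 97 per group, a reader of a null result cannot tell which effect the trial had a fair chance of finding.

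**Working it through.** **Inputs.** Control rate 0.25, the etanercept rates, 80% power and equal groups come from Section 4.3. The chi-square test comes from Section 7. Two-sided alpha 0.05 is assumed, with z = 1.960 for alpha and 0.842 for 80% power.

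**Formulas.** With d = p1 − p2 and p̄ the mean of the two rates, the uncorrected size per group is

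n = [1.960·√(2p̄(1−p̄)) + 0.842·√(p1(1−p1) + p2(1−p2))]² / d²

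and the continuity-corrected size is n_c = (n/4)·[1 + √(1 + 4/(n·d))]².

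**The plan's first table (80% power, control 0.25).**

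| Etanercept rate | Stated | Uncorrected | Corrected |
|---|---|---|---|
| 0.15 | 270 | 250.0 | 269.6 |
| 0.10 | 110 | 99.5 | 112.5 |
| 0.05 | 59 | 48.8 | 58.4 |
| 0.02 | 42 | 33.4 | 41.7 |

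Rounded up, the corrected formula gives three of the four entries and 113 where the plan has 110. The uncorrected formula gives none. Two-sided 0.05 with continuity correction is therefore a reasonable, though not exact, reading of how the first table was made.

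**The same method for 25% vs 8%.** Here p̄ = 0.165 and d = 0.17.

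- Uncorrected: (1.0288 + 0.4301)² / 0.0289 = 73.6, so 74 per group.
- Corrected: (73.6/4)·[1 + √(1 + 4/(73.6 × 0.17))]² = 85.0, so 85 to 86 per group.

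Neither is 97.

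**Power at the sizes in question** (two-sided 0.05, assumed). Chi-square power is given by normal approximation and by exact enumeration of all outcomes.

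| Rates | N per group | Corrected | Fisher | Chi-square, approx. | Chi-square, exact |
|---|---|---|---|---|---|
| 25% vs 8% | 97 | 85.6% | 87.5% | 89.7% | 91.0% |
| 25% vs 8% | 98 | 86.0% | 87.9% | 90.0% | 91.3% |
| 25% vs 10% | 98 | 73.5% | 75.2% | 79.4% | 80.7% |
| 25% vs 10% | 110 | 79.0% | 80.4% | 83.8% | 84.9% |
| 26% vs 10% | 98 | 78.4% | 80.0% | 83.6% | 84.8% |

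The 26% is the historical rate cited in Section 4.3 (52 of 200). For 25% vs 8% at 97 per group, the stated 80% is low by 5.6 to 11.0 points. For 25% vs 10%, going from 110 to 98 per group costs between 4.2 points (84.9 − 80.7) and 5.5 points (79.0 − 73.5).

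**Inputs that would give 97 or 98.**

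- 25% vs 9%, corrected: 97.4.
- 25% vs 10%, uncorrected with unpooled variance: 96.8.
- 25% vs 8% at 90% power, uncorrected: 98.1.
- A dropout allowance on the corrected size: 86/0.89 = 96.6 or 85/0.88 = 96.6.

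The protocol does not say which of these, if any, was meant.

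**The two totals.** 220 − 196 = 24 patients, or 24/220 = 11%. A dropout allowance would make the number recruited larger than the number completing. Here it is smaller, because 196 recruited cannot yield 220 completers.

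**The case against.** The strongest reply is that the failure to reproduce rests on inputs the protocol does not state. With an 11% to 12% dropout allowance, 97 per group leaves about 85 to 86 completers, and 80% is then right for 25% vs 8%. The note setting total enrolment at twice N heads the first table only, so it does not rule out an allowance in the second. The first table is also an imperfect benchmark, since the corrected formula gives 113 where it says 110. This stands in part. The row may hide an assumption rather than an arithmetic slip, but no allowance is stated anywhere, and as printed the four entries do not agree.

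Power rows may also have been lost when the text was extracted, so the absence of a range of effects should not be counted against the plan. That is fair. It does not explain why a row at 97 sits under a sentence that fixes N at 110.

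The 110 and 220 figures may be remnants of an earlier target, with 196 now governing. That is plausible, but the Primary Aim is current text and nothing says which number takes precedence.

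Finally, the consequence for power is limited. The row errs on the safe side, and under the Section 7 chi-square test 98 per group gives 79.4% to 80.7% for 25% vs 10%. This is correct and limits what can be claimed.

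**Conclusion.** The point holds, and the plan is wrong as written on two counts. First, 196 and 220 are both stated as the trial size. They differ by 24 patients, and dropout cannot reconcile them. This needs no assumption. Second, 80% power does not belong to 25% vs 8% with 97 per group. At two-sided 0.05 (assumed, and broadly supported by the first table) with no dropout allowance, power there is 85.6% to 91.0%, or the size for 80% is 74 to 86 per group. Which entry of the row is wrong cannot be settled from the protocol.

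This does not show a materially underpowered trial. For the 25% vs 10% effect behind the figure of 110, 98 per group gives 73.5% power with continuity correction and about 80% with the chi-square test. Any shortfall depends on the test and is small or nil under the one named in Section 7.

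**What to change.** State one size throughout. If it is 196 (98 per group), change the Primary Aim in Section 2, the two sentences in Section 4.3 that rest on 110, and the 220 in the Section 10 table. The other places already agree. If it is 220, change the Study Summary, the hypothesis statement in Section 2, and Sections 4 and 8.5.1.

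In Section 4.3, state alpha, sidedness, the test assumed and any dropout allowance, and recalculate both tables on that single basis, including the 110 entry. Unless the sponsor confirms that another effect, power or allowance was intended, the row at 196 would read: 25% vs 8%, 98 per group, about 86% (continuity-corrected) or 90% (chi-square). Add 25% vs 10% at 98 per group: about 74% (73.5% before rounding; corrected) or 79% (chi-square). The chi-square figures are the ones that match Section 7.

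The cost is a text and table correction. The test, endpoint and type I error do not change. Keeping 196 needs no extra patients, while choosing 220 means recruiting 24 more, plus any dropout allowance if 220 are to complete.
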